## 2. HYPOTHESES

The **primary** null ( $H_0$ ) and alternative ( $H_A$ ) statistical hypotheses are:

$H_{P0}$ : ART adherence as measured through an EMD throughout the six-month follow-up period will not differ between the intervention and standard of care arms.

$H_{PA}$ : ART adherence as measured through an EMD throughout the six-month follow-up period will be higher in the intervention arm compared to the standard of care arm.

The **first secondary** null ( $H_0$ ) and alternative ( $H_A$ ) statistical hypotheses are:

$H_{S10}$ : ART adherence as measured through biological measures will not differ between the intervention and standard of care arms.

$H_{S1A}$ : ART adherence as measured through biological measures will be higher in the intervention arm compared to the standard of care arm.

The **second secondary** null ( $H_0$ ) and alternative ( $H_A$ ) statistical hypotheses are:

$H_{S20}$ : Changes in self-reported ART adherence from baseline to the six-month follow-up period will not differ between the intervention and standard of care arms.

$H_{S2A}$ : Changes in self-reported ART adherence from baseline to the six-month follow-up period will be greater in the intervention arm compared to the standard of care arm.

The **third secondary** null ( $H_0$ ) and alternative ( $H_A$ ) statistical hypotheses are:

$H_{S30}$ : Uptake of OST at the six-month follow-up will not differ between the intervention and standard of care arms.

$H_{S3A}$ : Uptake of OST at the six-month follow-up will be higher in the intervention arm compared to the standard of care arm.

### 3. METHODS

This section contains information about the study design and statistical analysis that will be performed to assess the hypotheses.

#### 3.1. Study Design

We conducted a randomized controlled pilot trial of the adapted couple-based intervention. 66 couples were randomized into two arms – 33 couples into the intervention arm and 33 couples into standard of care (SOC). SOC consisted of an appointment with an AIDS Center nurse at baseline and three months and six months later. Under current SOC in Almaty, no behavioral intervention is provided. Participants obtain prescription refills and give blood for viral load and CD4 tests once every 6 months. Participants receive viral load and CD4 test results only by request, and adherence is generally not assessed. The intervention consisted of three sessions over the course of one month. Participants in both arms were assessed at four time points: baseline “pre-intervention”, immediately post-intervention (IPI), 3-month follow-up, and 6-month follow-up.

#### 3.2. Trial Randomization

#### 3.3. Data Sources

##### 3.2.1. Participant Surveys.

Participants completed surveys via Qualtrics at four timepoints -- baseline “pre-intervention”, immediately post-intervention (1-month after baseline), three-month and six-months follow-up. Among the many topics assessed, surveys included sociodemographic items, the validated self-reported three-item adherence scale, and use of OST.

##### 3.2.2. EMD Data.

HIV-positive participants were given an EMD that continuously monitored device openings. The EMD sends a signal to a secure website via cellular data networks whenever the device is opened as a proxy for ART adherence. If connection or SIM card problems prevent real-time monitoring, records and diagnostics are stored (up to 1 year) and uploaded to the server when a connection is re-established. The device can store a 30-day supply of medication.

### **3.2.3. Biological Measures.**

*Dried blood spot (DBS) samples* were collected from HIV-positive participants at their regular AIDS Center visit to assess feasibility and acceptability of the biological collection process and measure biological levels of medication. A nurse collected DBS samples by venipuncture, using a pipette to spot blood directly onto Whatman 903 ProteinSaver cards. The cards will be air-dried, individually packaged in a plastic bag with desiccant, and transferred to a -20 to -80°C freezer for storage. Only samples of participants on tenofovir-based regimens were shipped to the US.

*Hair samples.* Participants self-collected hair samples at baseline and immediately post-intervention to measure ART adherence levels. To collect hair samples, participants cut a small thatch of hair (~50 strands of hair) close to the scalp from a bottom layer of their hair. Hair was placed in a piece of tinfoil and inside a Ziploc bag labeled with their study ID. Participants shipped samples to GHRCCA staff, who then batch shipped samples to the US for testing.

*Viral load.* Participants are tested for viral load levels during every patient visit at the AIDS Center, which occurs every six months. Viral load data were abstracted from the AIDS Center electronic medical record at the closest visit prior to the baseline assessment and at the closest visit to the six-month follow-up assessment.

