4.4. Inclusion/Exclusion Criteria

Participant inclusion criteria

We will recruit 66 dyads (n=132) to participate in a randomized control trial of the adapted couple-based intervention. We anticipate we will need to screen 450 individuals to obtain 66 eligible dyads (n=132). Dyads are eligible to participate if

- (1) both partners are ≥ 18 years old,
- (2) both identify each other as their intimate partner, family member, friend, or other person within their social network,

- (3) the relationship has existed at least 3 months,
- (4) both report feeling safe participating with their partner in the study,
- (5) neither reports any severe physical or sexual violence perpetrated by the other partner in the past year,
- (6) both are able to provide informed consent and follow study procedures, and
- (7) both are fluent in Russian.

In addition, the “index case” (partner initially recruited from AIDS Center) must

- (1) be confirmed HIV+ by the AIDS Center,
- (2) have been on ART at least 3 months,
- (3) not be virally suppressed according to the AIDS Center standard (<500 copies/ml), and
- (4) report injecting any drug in the past year.

“Partners” may be HIV- or HIV+ and may or may not be a PWID. Because dyad dynamics may depend on the sex of the “index case”, women will be the “index case” in at least a third of dyads. If both partners meet eligibility criteria, both will provide consent, complete the baseline assessment, and be randomized to study arm.

Participant exclusion criteria

Individuals who do not meet inclusion criteria or who meet any of the following criteria will be excluded from the study.

- (1) unable to provide informed consent,
- (2) unwilling or unable to participate in study procedures,
- (3) any condition that, in the opinion of the principal investigator and research staff, would make participation in the study unsafe, complicate interpretation of study outcome data, or otherwise interfere with achieving the study objectives.

4.5. Study Enrollment. The Baseline Visit will be conducted remotely by phone or computer with participants. At the Baseline Visit, the participants will provide informed consent, be enrolled in the study, complete the baseline assessment through Qualtrics, and self-collect urine and hair samples (if HIV-positive), which will then be mailed to the GHRCCA research staff.

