#### 4.2. Dependent Variables

The dependent variables in this analysis are:

1. EMD measured ART adherence – Number of days EMD is opened from baseline to six-month follow-up (0 to 180 days) among participants in each arm.
2. Biological measures of ART adherence – Number of participants in each arm who are virally suppressed and adherent as measured through biological testing.
3. Self-reported ART adherence – Assessed by a validated three-item ART adherence scale. The three items are: 1) *Days taken* -- number of days the patient missed at least one dose of their medication (number of days, 0-30); 2) *Frequency* -- how often the patient took their medication in the way they were supposed to in the past 30 days (never/rarely/sometimes/usually/almost always/always); and 3) *Rating* – how good a job the patient did in taking their medication in the way they were supposed to in the past 30 days (very poor/poor/fair/good/very good/excellent). Responses were then linearly transformed into a scale of 0 to 100 (higher scores indicate greater adherence). The average score across the three items was calculated to represent overall adherence. Scale reliability among this sample was high (Cronbach's  $\alpha = .90$ ).
4. Uptake of OST – Number of participants who reported they were currently taking OST at the six-month follow-up.

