#### 4.6. Missing Data

The analysis sample is restricted to participants with data for the outcomes and with complete demographic information. Missing data for outcomes or demographics will not be imputed.

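### The follow-up viral load has no post-baseline condition and no window, so after a missed visit an early or pre-baseline test can stand as the six-month outcome

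*SAP*

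**What the plan says.** No study-specific viral load draw at follow-up is described. SAP 3.2.3 takes both values from the clinic record: the baseline value from the nearest visit before the baseline assessment, and the follow-up value "at the closest visit to the six-month follow-up assessment". The baseline value has a direction (before baseline). The follow-up value has only nearness.

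On frequency, SAP 3.2.3 says "Participants are tested for viral load levels during every patient visit at the AIDS Center, which occurs every six months", and SAP 3.1 says participants "give blood for viral load and CD4 tests once every 6 months". SAP 3.1 also says "SOC consisted of an appointment with an AIDS Center nurse at baseline and three months and six months later", which does not obviously fit a clinic visit every six months.

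The viral load feeds Secondary Outcome 1. SAP 4.2 counts suppressed participants per arm, and SAP 4.5 compares the counts by chi-square. Under Protocol 4.4 the index case must be unsuppressed at entry, with suppression defined as below 500 copies/ml. SAP 4.6 limits the analysis to participants with outcome data and adds: "Missing data for outcomes or demographics will not be imputed".

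Protocol 4.6.9 extracts a year of past viral load results but does not date the extraction.

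**The concern.** A nearest-visit rule without direction or limits gives a six-month value to anyone with a single test on record. If the nearest test was drawn while the sessions were still running, it cannot reflect the follow-up period. If it was drawn before baseline, it cannot reflect the intervention at all. For an index case such a value would usually read as not suppressed because of the entry criterion. It would work as a carried-forward baseline and so sidestep SAP 4.6, under which a participant without outcome data is left out. A count of suppressed participants gives no sign that some draws were mistimed. At stake is the suppression estimate in each arm, which a pilot is meant to pass on to the design of the larger trial.

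**Working it through.** The documents give no figure for the timing of these draws, so there is none to reproduce.

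**Inputs from the documents**
- Test interval: 6 months (SAP 3.1 and 3.2.3).
- Follow-up date F: month 6, from the 0-to-180-day count from baseline in SAP 4.2. Protocol 4.2 instead runs to six months after the intervention, which is about month 7 with a one-month intervention.
- Intervention period: one month (SAP 3.1), or up to two months from the first session (Protocol 4.6.2).
- 33 index cases per arm.

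**Assumptions**
- Clinic visits fall at a uniform phase relative to baseline.
- Each post-baseline visit is missed independently with probability p, taken as 10%, 20% and 30%.
- Attended visits are on time, and everyone has a test within the six months before baseline.
- Records after month 6 are available, except in step 4.

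**Step 1: on schedule.** On a six-month grid the nearest test is at most 3 months from F. That gives months 3 to 9 for F = 6, or 4 to 10 for F = 7. No pre-baseline or month 0-2 test is chosen. With uniform phase, 2/6 = 33% of draws fall within one month of F.

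**Step 2: when an early test wins.** A test at month t beats the next one, at t + g, when (t + g) − F > F − t, that is g > 2(F − t).

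| Earlier test at | Gap needed, F = 6 | Gap needed, F = 7 |
|---|---|---|
| month 2 | above 8 months | above 10 months |
| month 1 | above 10 months | above 12 months |
| baseline | above 12 months | above 14 months |

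One skipped visit makes the gap 12 months. With F = 6 that is enough to select any test drawn after baseline and before month 3. A test a months before baseline needs g > 12 + 2a, so at least two consecutive visits must be skipped.

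**Step 3: how often, F = 6.** Let u be the month of the first scheduled visit after baseline, uniform on 0 to 6. The others fall at u + 6 and u + 12, and the last pre-baseline test at u − 6.
- Draw in months 0-2: u < 2, visit u attended, visit u + 6 missed. Probability (2/6) × p(1 − p). For months 0-1 replace 2/6 by 1/6.
- Pre-baseline draw: visits u and u + 6 both missed, and for u < 3 also u + 12, which would otherwise be nearer. Probability (p² + p³)/2.

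| p | Pre-baseline | Months 0-1 | Months 0-2 |
|---|---|---|---|
| 10% | (0.01 + 0.001)/2 = 0.55% | 0.09/6 = 1.5% | 3.0% |
| 20% | (0.04 + 0.008)/2 = 2.4% | 0.16/6 = 2.7% | 5.3% |
| 30% | (0.09 + 0.027)/2 = 5.85% | 0.21/6 = 3.5% | 7.0% |

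Per arm of 33 this is 0.2 to 1.9 people scored on a pre-baseline test (33 × 0.0055 to 33 × 0.0585) and 1.0 to 2.3 on a month 0-2 test (33 × 0.030 to 33 × 0.070).

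**Step 4: records extracted at month 6 with nothing later.** The only candidates are u and u − 6. With no missed visits, 1/6 = 17% of draws fall in months 0-1, 2/6 = 33% in months 0-2, and none before baseline. At p = 10%, 10% are pre-baseline and (2/6) × 0.9 = 30% fall in months 0-2.

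**Step 5: weight of one participant.** 1/33 = 3.0 percentage points of an arm's suppression rate.

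**The case against.** The strongest reply is that the same paragraph of the SAP fixes a six-monthly schedule. A reader might infer that pre-baseline or mid-intervention tests would routinely be counted. Step 1 shows otherwise: on schedule, with later records available and sessions starting near baseline, neither happens. That stands.

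A reader might also say that the rule contradicts SAP 4.6. The documents do not go that far. The natural reading of SAP 3.2.3 is two separate abstractions, and 4.6 can be read as leaving out anyone with no follow-up test. But the SAP states a direction for the baseline value and none for the follow-up value, and nothing bars using one record for both. The intention is probably sound; the wording does not secure it.

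A third inference is bias between arms through changed clinic attendance. The documents do not make attendance a target or an outcome, and randomization balances visit phase in expectation. A difference between arms is possible but not shown.

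The frequencies rest on assumed missed-visit rates and a uniform phase. The nurse appointments at baseline, three and six months could tie testing to baseline and change them. That stands, so they show a range and do not predict what happened.

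Finally, a window of 3 months either side of month 6 is the on-schedule spread itself and does not narrow it. That is correct. What the window and the post-IPI condition remove is the early or pre-baseline value.

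**Conclusion.** The point holds as a gap in a stated rule, and it is minor. On the documents' own schedule the rule yields a draw in months 3 to 9. It fails for participants who miss or delay visits, or if extraction took place near month 6. Under assumed missed-visit rates of 10% to 30%, about 0.6% to 6% of participants would be scored on a pre-baseline test and 3% to 7% on a month 0-2 test. The documents supply no rate to narrow this. An extraction at month 6 would make early draws much more common, and the documents do not exclude it.

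The 3-point weight assumes one index case per dyad and all 33 in the denominator. HIV-positive partners, if counted, need not have been unsuppressed at entry. The effect is confined to one component of Secondary Outcome 1; the primary outcome, from the electronic monitoring device, is unaffected.

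**What to change.** In SAP 3.2.3, state that the follow-up viral load is the result closest to the six-month assessment, drawn after the IPI visit and no more than 3 months before or after that assessment. If there is no such result, the value is missing under SAP 4.6. Add a sensitivity analysis that counts missing as not suppressed. It gives an unsuppressed index case the same score as reusing the old test, but openly and as a labelled assumption.

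Also:
- Define the six-month date, reconciling 180 days from baseline (SAP 4.2) with six months after the intervention (Protocol 4.2).
- Reconcile the nurse appointments at baseline, three and six months with testing every six months, give the extraction date, and add a rule for ties.
- Report draw dates by arm, because the window leaves the month 3 to 9 spread in place.
- SAP 3.2.3 describes the abstraction in the past tense. If the rule is set after abstraction, say so.

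The cost is SAP wording, a re-run of the selection on existing records, and a few results that become missing. A tighter window would cost much more. With uniform phase, the share of on-schedule tests kept is 2w/6 for a window of w months either side: 33% (22 of 66 index cases) at 1 month, 67% (44) at 2 months, and all 66 at 3 months, subject to the post-IPI condition.

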### **3.4. Statistical Interim Analysis and Stopping Guidance**

There are no interim analyses or interim stopping rules that must be considered for this statistical analysis plan (SAP).

## **4. STATISTICAL PRINCIPLES AND ANALYSIS**

### **4.1 Confidence Intervals and P-values**

All statistical computations will be performed by the PI ([name]), who is an epidemiologist, in consultation with quantitative data scientists. For descriptive summaries of study data, the following will be presented:

- Nominal/categorical measures will be summarized using frequencies and percentages;
- Interval or ratio scale measures will be summarized using means and standard deviations;
- Ordinal measures will be summarized depending on the number of levels. An ordinal measure with five levels or less will be summarized as a nominal measure. An ordinal measure with more than five levels will be summarized as an interval or ratio scale measure.

The balance or imbalance of baseline characteristics will be studied and reported, particularly for analyses comparing the two study arms.

Reported p-values will be based on two-sided tests at an  $\alpha=0.05$  unless otherwise specified. When p-value correction is appropriate, Benjamini-Hochberg False Discovery Rate adjustments will be used to address multiplicity and preserve Type I error rate.

Unless required otherwise by a journal, the following rules are standard:

- Test statistics will be reported to two decimal places.
- P-values will be reported to two significant figures. If less than 0.001, p-values will be reported as '<0.001'.
- No preliminary rounding will be performed; rounding will only occur after analysis. To round, consider digit to right of last significant digit: if  $< 5$  round down, if  $\geq 5$  round up.

#### 4.2. Dependent Variables

The dependent variables in this analysis are:

1. EMD measured ART adherence – Number of days EMD is opened from baseline to six-month follow-up (0 to 180 days) among participants in each arm.
2. Biological measures of ART adherence – Number of participants in each arm who are virally suppressed and adherent as measured through biological testing.
3. Self-reported ART adherence – Assessed by a validated three-item ART adherence scale. The three items are: 1) *Days taken* -- number of days the patient missed at least one dose of their medication (number of days, 0-30); 2) *Frequency* -- how often the patient took their medication in the way they were supposed to in the past 30 days (never/rarely/sometimes/usually/almost always/always); and 3) *Rating* – how good a job the patient did in taking their medication in the way they were supposed to in the past 30 days (very poor/poor/fair/good/very good/excellent). Responses were then linearly transformed into a scale of 0 to 100 (higher scores indicate greater adherence). The average score across the three items was calculated to represent overall adherence. Scale reliability among this sample was high (Cronbach's  $\alpha = .90$ ).
4. Uptake of OST – Number of participants who reported they were currently taking OST at the six-month follow-up.

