In focus groups conducted with 58 HIV+ PWID in Kazakhstan, participants cited partner support as a key facilitator of ART adherence.³⁴ Participants stated that intimate partners provided needed support for dealing with their HIV status in a context where many of them are rejected by their families and experience high levels of stigma and discrimination for being HIV+ and a PWID from the community and healthcare providers as well.³⁴ Despite the desire for a couple-based approach, there is only one couple-based ART adherence EBI (SMART Couples), but it has not yet been adapted for PWID. The proportion of prescribed doses taken within a specified time window, as measured by MEMS Cap, was significantly greater among the intervention participants than control participants at 3 months (change score $b = -13.17$, $p=.028$).³⁵ The four-session SMART Couples intervention was designed to improve ART adherence among HIV+ patients by intervening with both the patient and his/her primary partner in order to foster support from the partner to achieve optimal adherence.³⁵⁻³⁷ While the intervention was shown to be effective in increasing the proportion of prescribed doses taken, its effects were short-lived.³⁵ Therefore, we propose to strengthen this promising and well-developed intervention to make it more relevant for PWID by integrating other existing efficacious adherence intervention strategies for PWID (i.e., directly observed therapy, drug risk reduction components)^{38,39}, incorporating linkage to opioid substitution therapy (OST), and adding new biomedical tools that provide an objective measure of adherence and may provide greater utility in a clinical setting than current adherence monitoring tools (i.e., electronic monitoring devices). The adaptation of an existing, efficacious couple-based adherence intervention strategy for PWID, combined with the integration of efficacious individual-level adherence strategies (i.e., directly observed therapy (DOT)) modified for couples and the incorporation of linkage to drug treatment services and needle-exchange programs could substantially improve adherence among HIV+ PWID, especially in resource constrained settings. Additionally, measuring adherence over time through the use of a mobile app and through new biomedical strategies to measure adherence (i.e., dried blood spot (DBS) tests) could provide a more objective measure of adherence, allowing earlier detection of adherence problems and more timely intervention.

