4.6.3. Immediately Post-Intervention (IPI) Visit (for all participants)

The IPI will be conducted by phone/video call or in-person in GHRCCA’s field office (post-COVID). Prior to the visit, an RA will mail an IPI kit to participants containing materials to self-collect hair and urine samples. For in-person visits, participants will self-collect samples at the GHRCCA field office. The following procedures/assessments will be performed at the IPI visit:

1. The RA will verify the participants by the name on the record and update the **Locator Information Form**;
2. The RA will send the **IPI Assessment** through Qualtrics;
3. The RA will conduct an **EMD** test and will check in with the participant regarding EMD uses and resolve any issues;
4. Participants will self-collect urine samples and hair samples to measure biological levels of medication adherence. These samples will be mailed to GHRCCA staff.
5. At the participant’s next regular AIDS Center visit, the nurse will obtain an additional **blood sample** to conduct dried blood spot sampling and measure levels of medication in the body

4.6.4. 3-month and 6-month Follow-Up Visits (for all participants)

Three- and six-month Follow-Up Visits will be conducted by phone/video call or in-person in GHRCCA’s field office (post-COVID). The following procedures/assessments will be performed at the 3- and 6-month follow-up visits:

1. The RA will verify the participants by the name on the record and update the **Locator Information Form**;
2. The RA will send the **3- or 6-month follow-up assessment** through Qualtrics;
3. At the **3-month** follow-up, the RA will conduct an **EMD** test and will check in with the participant regarding EMD uses and resolve any issues. At the **6-month** follow-up, the participant will mail the **EMD** back to the RA.
4. After the **6-month** follow-up, the RA will administer the Exit Interview;

4.6.5. Pilot study assessments. Participants in both arms will receive the same schedule of assessments. There will be four main repeated assessment occasions: baseline “pre-intervention”, immediately post-intervention (IPI), 3-month and 6-month follow-up. The primary adherence outcome will be proportion of prescribed doses taken as measured by EMD. Study assessments will be delivered remotely through Qualtrics.

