4.6.6. Electronic Monitoring Device (EMD) Data. We will continuously monitor EMD device openings. The EMD sends a signal to a secure website via cellular data networks whenever the device is opened as a proxy for ART adherence. If connection or SIM card problems prevent real-time monitoring, records and diagnostics are stored (up to 1 year) and uploaded to the server when a connection is re-established. The device can store a 30-day supply of medication. EMD-measured adherence will be operationalized as percentage of days/doses for which a device-opening signal was received in the past month. EMDs will be given to participants in both arms. Pills will be deposited into the EMD device, which will record every time the device is opened. EMD data will allow patients to see objective feedback of their adherence patterns, which could help them improve their medication adherence.

At the conclusion of the baseline visit, the RA will mail the participant an EMD device with instructions on how to fill the device, open it for dosing, and pair it with the app. The RA will call the participant to assist with troubleshooting and confirm that the EMD device is properly set up, that it is recognized by the EMD server, and that device openings are being recorded properly (date and time). If 7 days pass and the device is not seen at all on the server, the RA will call the participant to see if there are any device problems. At each study visit, the RA will ask if the participant is having any problems using the EMD.

4.6.7. Weekly app assessments on a mobile phone. Based on GHRCCA’s previous studies, we anticipate that participants will own a smart phone. We will pay for all participants’ data plans during the course of the study. Weekly assessment data will be collected once a week throughout the course of the study through an app which will be installed on participants’ phones. Assessment items will focus on drug use in the past week, adherence to ART, social support, and relationship satisfaction.

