#### 4.5. Statistical Analysis Methods

Descriptive statistics of key independent variables and covariates will be summarized within each arm using frequencies or means (standard deviations) as appropriate. Overall participation rates will be reported in each arm based on the proportion of baseline participants who completed the six-month follow-up assessment.

To test **hypothesis 1 (H1)**, we will conduct t-tests to assess for differences in ART adherence rates over six months (0 to 180 days) between study arms.

To test **hypothesis 2 (H2)**, we will conduct chi-square tests to assess for differences in biological measures of ART adherence between study arms. Adjustments for small sample sizes will be made as appropriate.

To test **hypothesis 3 (H3)**, we will conduct generalized linear mixed modeling to assess for change in self-reported ART adherence from baseline to the six-month follow-up period and compare between arms. Generalized linear mixed modeling will be used to account for the effect of response clustering within participants. Models will adjust for the covariates specified above (section 4.4) and include random effects for dyad and intercept.

The model testing H3 is summarized as Equation H3:

$$\begin{aligned} \text{ART adherence} = & \text{Intercept} + B_1(\text{Arm}) + B_2(\text{Categorical variable corresponding to timepoint of adherence assessment; two degrees of freedom}) + \\ & B_3(\text{Arm * Timepoint of adherence assessment; two degrees of freedom}) + B_4(\text{Baseline adherence level}) + B_5(\text{Partner HIV status}) + B_6(\text{Respondent Age}) + B_7(\text{Respondent Sex}) + \text{Error} \\ & + \text{Random effects for the clustering within participant across timepoints and by dyad.} \end{aligned}$$

If the statistical test for the interaction between arm and timepoint is significant at the  $\alpha=0.05$  level, then we conclude that study arm significantly impacts the change in ART adherence. Within arm, adjusted estimates of changes in adherence will be presented along with 95% confidence intervals.

To test **hypothesis 4 (H4)**, we will conduct chi-square tests to assess for differences in uptake of OST between study arms. Adjustments for small sample sizes will be made as appropriate.

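### The SAP's primary EMD variable, a 0 to 180 day count, departs without explanation from the protocol's percentage of doses and leaves partial records and HIV-positive partners unresolved

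*SAP*

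**What the plan says.** **Protocol.** Section 4.6.5 states: "The primary adherence outcome will be proportion of prescribed doses taken as measured by EMD". It gives no window. Section 4.6.6 operationalises EMD adherence as the "percentage of days/doses for which a device-opening signal was received in the past month". Section 4.7 also names a one-month adherence percentage among the parameters the pilot should estimate.

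**SAP.** Section 4.2 defines the primary variable as "Number of days EMD is opened from baseline to six-month follow-up (0 to 180 days) among participants in each arm". Section 4.5 says "we will conduct t-tests to assess for differences in ART adherence rates over six months (0 to 180 days) between study arms". Sections 1, 2, 4.2 and 4.5 all refer to six months, so the SAP does choose a window. It does not say why it left the past month.

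**Missing data.** SAP 4.6 reads: "The analysis sample is restricted to participants with data for the outcomes and with complete demographic information". It adds: "Missing data for outcomes or demographics will not be imputed". Neither sentence says whether a partly recorded EMD history counts as outcome data.

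**Who is counted.** SAP 3.2.2 gives devices to HIV-positive participants. Protocol 4.4 allows partners to be HIV-positive. SAP 4.2 counts participants in each arm, not index cases. SAP 4.4 lists the partner's HIV status as a covariate, which suggests that the index case is the unit.

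**The concern.** This is the variable on which the primary null hypothesis is tested. The same device logs can give different results depending on the window, on how unmonitored days are scored and on whether partners are included.

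- **Window.** The protocol says of the parent intervention: "While the intervention was shown to be effective in increasing the proportion of prescribed doses taken, its effects were short-lived". An average over six months and a past-month percentage then measure different things.
- **Unmonitored days.** On a fixed 180-day scale, a day after device loss or withdrawal looks the same as a missed dose. If one arm loses more people, that difference becomes an apparent adherence effect.
- **Partners.** If both members of some dyads contribute, a two-sample t-test treats correlated observations as independent. The SAP includes a dyad effect for self-reported adherence but not for this test.
- **Demographics.** SAP 4.6 removes randomised participants who lack demographic data from a primary test that uses no demographics.

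Protocol 4.7 gives accurate parameters for the next trial as a main purpose of the pilot, so the chosen definition carries forward.

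**Working it through.** The plan gives no figure for the 0 to 180 count. Its only related number is in Protocol 4.6.12: 80% power for f = 0.15 with 60 dyads by repeated-measures ANOVA. With four assessments and assumed correlation 0.5 and sphericity, the noncentrality is 0.15² × 60 × 4 / 0.5 = 10.8 on 3 and 174 degrees of freedom. Power is then 0.786, close to the stated value. That calculation does not settle how the EMD variable is defined. The rest is illustrative, because the documents give no adherence level, SD, loss by arm or share of HIV-positive partners.

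**1. Count versus percentage.** Under full monitoring, percentage = 100 × count / 180 for everyone. The t statistic is unchanged, so the change of unit alone does no harm. Days and doses differ only if some regimens are not once daily, which the documents do not say.

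**2. Window.** Protocol 1.5 reports that adherence in the parent trial was "significantly greater among the intervention participants than control participants at 3 months", with a change score of size 13.17. I use 13.17 percentage points only as a scale. Past-month values are averaged over the three follow-up assessments (days 1–30, 61–90 and 151–180).

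| Assumed course of effect | Six-month mean | Past-month, mean of three visits |
|---|---|---|
| Constant | 13.2 | 13.2 |
| Starts after day 30, lasts | 13.17 × 150/180 = 11.0 | (0 + 13.17 + 13.17)/3 = 8.8 |
| Stops at day 90 | 13.17 × 90/180 = 6.6 | (13.17 + 13.17 + 0)/3 = 8.8 |
| Linear fade to zero at day 180 | 13.17/2 = 6.6 | (12.07 + 7.68 + 1.10)/3 = 7.0 |

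The windows differ, but moderately.

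**3. Partial records.** A participant with 81 openings in 90 monitored days scores 81/180 = 45% on the fixed scale and 81/90 = 90% on monitored days, or is excluded.

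*No true effect.* Assume 33 per arm, 70% adherence in both arms, exit at day 90 by 5% versus 15%, and leavers still on ART. Scoring lost days as unopened gives a false gap of (0.15 − 0.05) × 0.70 × 90 = 6.3 days. In simulations of 20,000 trials with SD 20 to 30 points:

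- lost days scored as unopened: type I error about 8% to 10%;
- leavers excluded, or monitored-day denominator: about 5%;
- equal 10% loss: about 5% under all three.

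*True 80% versus 65%.* The true gap is 144 − 117 = 27 days. Scoring lost days as unopened gives:

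- equal 10% loss: 27 × 0.95 = 25.7 days;
- 5% intervention, 15% standard of care: 0.80 × 175.5 − 0.65 × 166.5 = 32.2 days;
- 15% intervention, 5% standard of care: 0.80 × 166.5 − 0.65 × 175.5 = 19.1 days.

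At SD 25 points, power in these three cases is about 57%, 77% and 36%. It is about 66% throughout with a monitored-day denominator.

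If leavers in fact stopped ART, the ranking reverses: zero is then the right score, and the other two methods miss the gap.

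**4. Partners.** Let a share s of partners be HIV-positive, with within-dyad correlation r. The variance of an arm mean is inflated by 1 + 2sr/(1 + s), and the type I error is about 2 × [1 − Φ(1.96/√inflation)].

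- s = 0.5, r = 0.2: inflation 1.133, about 6.6%.
- s = 0.5, r = 0.5: inflation 1.333, about 9.0%.
- s = 1, r = 0.5: inflation 1.5, about 11%.
- r = 0: 5%.

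Simulation with 33 dyads per arm agrees within about 0.3 points.

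**The case against.** Much can be said for the SAP. It states its window consistently, and Protocol 4.2 has EMD data collected throughout intervention and follow-up, so six months is a natural choice. Protocol 4.6.6 already allows days or doses. The 0 to 180 range beside the word rates can be read as a fixed denominator of 180. Scoring unmonitored days as unopened is itself a form of imputation, which SAP 4.6 rules out. The partner covariate points to index cases only. This is also a pilot, concerned mainly with safety, acceptability and feasibility.

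All of this limits the point without removing it. A reason for leaving the protocol's definition is still missing. SAP 4.6 can be read against zero-scoring but does not say what happens to a partial record. The covariate list describes adjusted models, not the t-test.

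Three stronger readings are tempting, and the documents do not support them:

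- **The change was made after results were seen.** SAP 1 and 3.1 are in the past tense, and SAP 4.2 reports scale reliability in this sample, so survey data existed. That does not show that EMD data had been seen by arm, and SAP 4.5 is in the future tense. The SAP's title page was not in the text reviewed, so nothing can be said about its date.
- **The two windows give wholly different answers.** That impression comes from taking the past month at month 6 alone. The protocol assesses three times after baseline, and averaging over those visits brings the windows much closer.
- **The primary test is biased.** That needs unequal loss, a particular scoring of lost days and leavers still on ART. None of these is established. Connection failures are not a cause, because stored records upload later.

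**Conclusion.** The point holds as a needed clarification of the primary endpoint; it does not demonstrate bias. The departure from the protocol's definition is plain on the text and unexplained. Confidence is high that the window change is unexplained and that partial records and partners are not settled.

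The sizes are illustrative. Type I error is about 8% to 10% if lost days score as unopened, loss is 5% versus 15% at day 90 and leavers remain on ART; with equal loss it is about 5%. It is about 6.5% to 9% if half of partners are HIV-positive with within-dyad correlation 0.2 to 0.5 and dyad is ignored; it is 5% if the correlation is zero or only index cases are analysed. The complete-demographics restriction is a smaller matter and probably affects few people.

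**What to change.** In SAP 4.2 and 4.5:

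1. Define the primary variable as the percentage of monitored days (or prescribed doses) with an opening over the stated six-month window. Define monitored time, for example from confirmed set-up to device return, loss or withdrawal.
2. Report the 180-day count and monitored days by arm beside it, because neither measure is right if leavers' ART use is unknown.
3. Report the protocol's past-month percentage immediately post-intervention and at 3 and 6 months, with 95% confidence intervals.
4. Restrict the primary test to index cases, or account for dyad if partners are included.
5. Apply the complete-demographics restriction only to adjusted models.
6. Give the reason for the change from Protocol 4.6.5 and 4.6.6, and say whether EMD data by arm had been seen. If they had, label the revised definition post hoc and keep the SAP's count result in the report.

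The cost is SAP wording and reprogramming from the existing device logs; no new data are needed. The downside is that a monitored-day percentage assumes unmonitored time resembles monitored time. Days of device failure can be set aside only where the failure was dated. The documents describe stored diagnostics and troubleshooting calls, but no dated failure log.
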